### **6.10 Week 14:**

Patients with **unilobar disease** that **did undergo** a **second session of TACE** will undergo a contrast enhanced MR or CT, IR clinical office visit and response assessment. At the clinical office visit - compliance with HCQ therapy, toxicity and AEs will be recorded.

Patients with **bilobar disease** and patients with **unilobar disease that did not undergo a second session of TACE** will not have any required study procedures at this time point.

### **6.11 Follow-Up Q3 Months:**

Study follow-up of patients will occur at 3 months (+/- 1 week) and 6 months (+/- 1 week) after cessation of HCQ therapy (Week 12 or Week 14). The 3 month and 6 month follow-up visits will include contrast enhanced MRI or CT, laboratory assessments (CBC, PT/INR, CMP) and IR clinical office visits by an interventional radiologist. The follow-up study period will end at 6 months (+/- 1 week) after cessation of HCQ therapy (Week 12) to examine for late toxicity. Patients will continue to be followed beyond the end of follow-up study period per normal Interventional Radiology standard of care and *only* patient data regarding tumor progression and survival will be recorded during this time period to better assess LPFS and overall survival.

## **7 Statistical Plan**

### **7.1 Study Objectives, Sample Size Determination and Power Calculation**

#### **Objectives**

This trial is designed to be the initial prospective phase I-II investigation of the safety and effectiveness of combined HCQ and TACE for unresectable HCC.

Primary Objective (Phase I): To determine the dose limiting toxicities and maximum tolerated dose (MTD) of the oral administration of hydroxychloroquine (HCQ) in conjunction with transarterial chemoembolization (TACE) in treating unresectable hepatocellular carcinoma (HCC). A "3+3" design will be used.

Primary Objective (Phase II): To evaluate the complete response rate in a cohort of patients treated at the MTD. A Simon's Optimal Two Stage design will be used.

The knowledge gained from this phase I-II clinical trial will establish the safety of combined therapy and allow for accurate estimate of the number of patients needed to adequately power larger phase II and III clinical trials.

#### **Sample Size Determination and Power Calculation**

In the reported literature, the rate of complete necrosis of HCC ranges from 29-43% even after repeated TACE(9,13,15-20). Georgiades, et al., studied the radiologic responses of 116 patients who underwent TACE(21). After a second TACE, the complete radiologic response rate increased from 14 to 38%. However, still over 25% of the patients did not respond at all to two TACE treatments, and 62% of patients did not have a complete response by imaging (see Imaging Assessment of Response under Section 3.3)(21).

Using a Simon's optimal two-stage model, the efficacy of combined therapy at increasing complete imaging response rate will be tested. The null hypothesis that the complete response rate of TACE and HCQ will be similar to TACE alone ( $p_0 = 40\%$ ) will be tested against a one-sided alternative, the complete

CONFIDENTIAL

This material is the property of the University of Pennsylvania. Do not disclose or use except as authorized in writing by the study sponsor

response rate of combined TACE and HCQ will be 60% ( $p_1$ ). In the first stage, 16 patients will be accrued, of which 6 will be patients treated at the MTD in the phase I trial. If there are 7 or fewer complete responses in these 16 patients, the study will be stopped. The probability of stopping the trial after the first stage of the Simon's optimal design is 72%. Otherwise, 30 additional patients will be accrued for a total of 46 patients. The null hypothesis will be rejected if 23 or more responses are observed in 46 patients. This design yields a type I error rate of 0.05 and power of 0.80 when the complete response rate of combined TACE and HCQ is 60%.

Thus, the maximum number of patients needed to complete the trial will be approximately 58. If all 3 dose levels are investigated in the Phase I trial, 18 patients will be required. Forty patients will be needed to complete the Phase II component, of which 6 will be patients treated at the MTD in the Phase I trial.

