Statistical Methodology	Phase I: To determine dose limiting toxicity and maximum tolerated dose of HCQ in combination with TACE. Basic statistical analysis will include tabulation of graded toxicities by dose level.  Phase II: Using Simon's optimal Two Stage design, we evaluate the efficacy of the combination of HCQ and TACE at the MTD to induce complete response as determined by mRECIST imaging criteria. Study is powered to detect a 20% increase in complete response rate (i.e. complete necrosis) from 40% to 60%.

CONFIDENTIAL

This material is the property of the University of Pennsylvania. Do not disclose or use except as authorized in writing by the study sponsor

Principal Investigators	[name] (IR) [name] PhD (IR)
Sub-Investigators/Key Personnel	[name] (IR) [name] PhD (IR) [name] (Hepatology) [name] PhD (Radiology) [name] (Hematology Oncology) [name] (Hematology Oncology) [name] (Hematology Oncology) [name] (Radiology) [name], MS (Radiology Director Research Operations) [name], BS (Radiology, Research Coordinator) [name], MS, CCRP (IR Research Project Manager) [name], BSN (IR Research Coordinator) [name], MS (Biostatistician)

CONFIDENTIAL

This material is the property of the University of Pennsylvania. Do not disclose or use except as authorized in writing by the study sponsor

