## 7.2 Statistical Methods

Phase I: Frequency of reported side effects and DLTs will be graded according to the Common Terminology Criteria of Adverse Events (CTCAE) version 4.0 and tabled by dose level. Additionally, the timing of these events relative to the first or second TACE will also be tabled by dose level.

Phase II: At the MTD, complete response rate to therapy and 95% confidence intervals will be calculated. Local progression free survival and overall survival curves will be estimated by the Kaplan-Meier method.

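### The Phase II rejection threshold is one response too low: rejecting at 23 of 46 gives a one-sided type I error of 7.7%, not the stated 5%

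*Combined protocol and SAP*

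**What the plan says.** Section 7.1 (Sample Size Determination and Power Calculation) sets a null complete response rate of 40%, which "will be tested against a one-sided alternative, the complete" response rate being 60%. On stage 1 it says "In the first stage, 16 patients will be accrued, of which 6 will be patients treated at the MTD in the phase I trial", and "If there are 7 or fewer complete responses in these 16 patients, the study will be stopped". The chance of stopping there is given as 72%. If the trial continues, 30 more patients bring the total to 46. The final rule is "The null hypothesis will be rejected if 23 or more responses are observed in 46 patients", followed directly by "This design yields a type I error rate of 0.05 and power of 0.80" at a true rate of 60%.

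Section 3.1 (Phase II, Simon's Two Stage Design) repeats the same final rule, the same error rates and the same 72%. No other section gives a different final cut-off.

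**The concern.** Simon designs are usually written r1/n1 and r/n, where r1 and r are the largest counts at which the treatment is not taken forward. The plan reads the stage 1 bound that way: 7 or fewer stops the trial. At the final analysis it treats the corresponding bound, 23, as the first count that rejects. If that is a slip, the threshold and the error rates in the next sentence belong to two different rules.

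The consequence is direct. Phase II has a single arm and no concurrent control, so this count alone separates a positive from a negative result on the primary endpoint. If the ambiguity were found only after a result of 23 of 46, neither reading could be chosen credibly.

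**Working it through.** **Inputs** (all from section 7.1): p0 = 0.40, p1 = 0.60, one-sided; n1 = 16, stop if X1 ≤ 7; n2 = 30, n = 46; reject if the total is at least c, with c = 23 as printed.

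**Step 1. The stated stopping probability.** P(X1 ≤ 7), with X1 ~ Bin(16, 0.40), is 0.716. This reproduces the stated 72%. It does not depend on the final cut-off.

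**Step 2. Rejection probability.** The trial rejects only if it passes stage 1 and then reaches c in total:

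P(reject | p) = Σ over x = 8,…,16 of P(X1 = x) × P(X2 ≥ c − x), with X1 ~ Bin(16, p) and X2 ~ Bin(30, p).

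The terms at p = 0.40 are:

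| x | P(X1 = x) | P(X2 ≥ 23 − x) | product, c = 23 | P(X2 ≥ 24 − x) | product, c = 24 |
|---|---|---|---|---|---|
| 8 | 0.14167 | 0.17537 | 0.02484 | 0.09706 | 0.01375 |
| 9 | 0.08395 | 0.28550 | 0.02397 | 0.17537 | 0.01472 |
| 10 | 0.03918 | 0.42153 | 0.01651 | 0.28550 | 0.01118 |
| 11 | 0.01425 | 0.56891 | 0.00810 | 0.42153 | 0.00601 |
| 12 | 0.00396 | 0.70853 | 0.00280 | 0.56891 | 0.00225 |
| 13 to 16 | 0.00094 | – | 0.00079 | – | 0.00069 |
| **Sum** | | | **0.0770** | | **0.0486** |

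The same sum at p = 0.60 gives the power:

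| Final rule | Type I error (p = 0.40) | Power (p = 0.60) |
|---|---|---|
| 23 or more of 46 (printed) | 0.0770 | 0.8290 |
| 24 or more of 46 | 0.0486 | 0.8006 |
| Stated in the plan | 0.05 | 0.80 |

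A threshold of 24 reproduces both stated figures; 23 reproduces neither.

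**Step 3. Where the 23 comes from.** A full search over two-stage designs for 0.40 versus 0.60, with type I error at most 0.05, power at least 0.80 and n up to 60, minimising expected sample size under p0, returns r1/n1 = 7/16 and r/n = 23/46. The expected sample size is 16 + (1 − 0.716) × 30 = 24.5. In that search, rejection means more than r responses, so it begins at 24.

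**Step 4. Could another reading rescue 23?**
- Ignoring the stage 1 stop (a single stage of 46, reject at 23 or more): type I error 0.109, power 0.936.
- Taking stage 1 as 12 patients, a figure that also appears in section 3.1, with the same bound of 7 and total of 46: type I error 0.024, power 0.432. The stopping probability would be 0.943, not 72%.

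Neither gives 0.05 and 0.80. The 12 in section 3.1 is a separate inconsistency: the same paragraph goes on to refer to 16 patients, and 16 + 30 = 46.

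**Step 5. Size of the difference.** The two rules differ only when the trial passes stage 1 and ends on exactly 23 responses. The probability of that is 0.0770 − 0.0486 = 0.028 at a true rate of 40%, and 0.8290 − 0.8006 = 0.028 at 60%. At a true rate of 50% it is 0.073.

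**The case against.** The arithmetic on the cut-off has no answer in the documents. What can fairly be said is that its reach is limited. Only one final outcome, 23 of 46, is classified differently. The absolute excess over the stated type I error is 2.7 percentage points (0.077 − 0.05). The stage 1 rule, the sample size and patient exposure are unaffected. This is also an initial single-arm phase I–II study meant to inform larger trials, so no confirmatory claim hangs on it. All of that is true, and it limits the harm. It does not remove the contradiction between two adjacent sentences.

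A related worry about section 7.2, where "complete response rate to therapy and 95% confidence intervals will be calculated", is much weaker. A two-sided 95% interval can include 40% when the one-sided 5% test rejects. If the ordinary exact (Clopper-Pearson) interval is assumed, it runs from 36.9% to 67.1% at 24 of 46 and from 39.0% to 69.1% at 25 of 46. But section 7.2 names no method, and at 25 of 46 the Wilson lower limit is 40.2%, which excludes 40%. The decision also rests on the count, not the interval, and reporting a two-sided 95% interval beside a one-sided 5% test is common. That objection stands: the interval is a matter of optional refinement, not an error.

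**Conclusion.** The concern holds. The final rule in sections 3.1 and 7.1 has a one-sided type I error of 0.0770, about 1.5 times the stated 0.05 (0.077 / 0.05 = 1.54), and power of 0.829 instead of 0.80. The sample sizes, the stage 1 bound and the 72% all agree with the Simon optimal design, so the error is confined to the final cut-off. It must be corrected, because it is the final success criterion for the Phase II primary endpoint.

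The result is exact. It assumes only independent binomial responses, 16 patients in stage 1, and a stage 1 stop that is followed as written. The conclusion rests on the cut-off alone and not on the choice of confidence interval.

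**What to change.** In both section 3.1 and section 7.1, change the final rule so that the null hypothesis is rejected at 24 or more responses in 46 patients (more than 23). Leave the stage 1 bound of 7 in 16, the total of 46 and the stated error rates as they are. If the sponsor prefers to keep 23, both sections should state a type I error of 0.077 and power of 0.83. Either change should be made before Phase II responses are known.

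The cost is one number in two paragraphs. No patients are added, and power moves from the 0.829 of the printed rule to the 0.80 already promised.

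Optionally, section 7.2 could name the interval method and give an estimate and a 90% two-sided interval that allow for the two-stage sampling, so that interval and test agree. The correction above does not depend on this.

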## 7.2 Statistical Methods

Phase I: Frequency of reported side effects and DLTs will be graded according to the Common Terminology Criteria of Adverse Events (CTCAE) version 4.0 and tabled by dose level. Additionally, the timing of these events relative to the first or second TACE will also be tabled by dose level.

Phase II: At the MTD, complete response rate to therapy and 95% confidence intervals will be calculated. Local progression free survival and overall survival curves will be estimated by the Kaplan-Meier method.

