## Study Summary

Title	Phase I-II Clinical Trial of the Safety and Preliminary Efficacy of Hydroxychloroquine combined with Transarterial Chemoembolization in Unresectable Hepatocellular carcinoma
Short Title	Phase 1-2 Trial HCQ plus TACE in Unresectable HCC
Protocol Number	UPCC 22213
Phase	Phase 1-2
Methodology	Single arm, unblinded, dose escalation
Study Duration	5 years
Study Center(s)	Hospital of the University of Pennsylvania
Objectives	Primary Phase I: To determine dose limiting toxicities and maximum tolerated dose (MTD) of the oral administration of hydroxychloroquine (HCQ) in conjunction with transarterial chemoembolization (TACE) in treating hepatocellular carcinoma (HCC) Primary Phase II: To evaluate the tumor necrosis rate in a cohort of patients treated at the MTD
Number of Subjects	Maximum 58 [18 patients maximum (6 patients at 3 dose levels) to define maximum tolerated dose (MTD) and total of 46 patients as expansion of cohort at the MTD, which includes 6 patients at MTD from Phase I]
Diagnosis and Main Inclusion Criteria	≥18yo, unresectable HCC, outside transplant criteria Candidate for TACE for palliative therapy Exclusions: HCQ allergy, porphyria, uncontrolled psoriasis, and existing retinopathy
Study Product, Dose, Route, Regimen	Hydroxychloroquine: Initial Dose 400mg PO daily for 28 days prior to TACE and continued until 8 weeks (2mo) following initial TACE. Doses will be escalated to, 400 mg BID (9AM/9PM), and 600 mg BID ( 9AM/9PM) to define MTD.  Phase I: Dose escalation will be performed to define dose limiting toxicities and maximum tolerated dose (MTD) using 3+3 cohort expansion design.  Phase II: Expansion of cohort at MTD using Simon's optimal Two Stage design to define complete response rate as determined by mRECIST imaging criteria. Study will be powered to detect a 20% increase in complete response rate (i.e. complete necrosis) from 40% to 60%.
Duration of administration	12-15 weeks
Reference therapy	TACE without HCQ

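### The 95% confidence interval planned for the complete response rate is not tied to the one-sided 5% two-stage test, so the trial can reject 40% while its interval contains 40%

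*Combined protocol and SAP*

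**What the plan says.** Section 7.1 (Sample Size Determination and Power Calculation) sets up the decision: "Using a Simon's optimal two-stage model, the efficacy of combined therapy at increasing complete imaging response rate will be tested". The null rate of 40% "will be tested against a one-sided alternative" of 60%. The first stage has a futility stop: "If there are 7 or fewer complete responses in these 16 patients, the study will be stopped". Otherwise 30 more patients are accrued, and the null is rejected from 23 responses in 46. The stated properties are "This design yields a type I error rate of 0.05 and power of 0.80", with a 72% chance of stopping after stage 1.

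Section 7.2 describes the reported result: "At the MTD, complete response rate to therapy and 95% confidence intervals will be calculated". It does not name an estimator, an interval method or a sidedness, and it does not refer to the stages. Section 7.3 adds that the analysis is by intention to treat. No other section links the interval to the test.

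**The concern.** The test spends 5% on one side and takes account of the stage 1 stop. An ordinary two-sided 95% interval spends 2.5% per side and treats the data as one fixed sample. Two procedures with different error rates and different sampling models need not agree on whether 40% is excluded. A report could then announce that 40% is rejected beside an interval that includes 40%, on the primary endpoint, with nothing in the plan to say which statement governs. The result also has a further use: section 7.1 says the trial will "allow for accurate estimate of the number of patients needed to adequately power larger phase II and III clinical trials". How the response rate and its uncertainty are reported should therefore be fixed in advance.

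**Working it through.** **Inputs** (section 7.1): p0 = 0.40, p1 = 0.60; stage 1 n = 16, stop at 7 or fewer; stage 2 n = 30; total 46; rejection from R = 23 as written. Section 3.1 first gives 12 patients for stage 1 and then refers to 16. I use 16, as in 7.1, because it reproduces the 72%. By intention to treat, the denominator is taken as 16 or 46.

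**Step 1: the plan's own figures.**
- Early stopping at 40%: P(Bin(16, 0.40) ≤ 7) = 0.716, which reproduces 72%.
- P(reject; R, p) = Σ over x = 8 to 16 of P(Bin(16, p) = x) × P(Bin(30, p) ≥ R − x).
- R = 23 (as written): 0.0770 at p = 0.40 and 0.829 at p = 0.60. The stated 0.05 is not reproduced.
- R = 24: 0.0486 and 0.8006. This reproduces 0.05 and 0.80. A search for Simon's optimal design returns 7/16 and 23/46 with rejection above 23.

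**Step 2: ordinary two-sided 95% intervals against 40%.**

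| Responses | Two-stage p | Clopper-Pearson | Wilson lower | Wald lower |
|---|---|---|---|---|
| 23/46 | 0.0770 | 34.9–65.1% | 36.1% | 35.6% |
| 24/46 | 0.0486 | 36.9–67.1% | 38.1% | 37.7% |
| 25/46 | 0.0281 | 39.0–69.1% | 40.2% | 39.95% |
| 26/46 | 0.0149 | 41.1–71.1% | 42.3% | 42.2% |

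At 23 and 24 all three methods contain 40%. At 25, Clopper-Pearson and Wald do and Wilson does not. From 26 there is no conflict.

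**Step 3: how often, as a share of rejecting trials.**
- Clopper-Pearson, rejection from 24, conflict at 24 and 25. True 50%: 0.1546 / 0.3601 = 43%. True 60%: 0.1130 / 0.8006 = 14%.
- Clopper-Pearson, rejection from 23 as written, conflict at 23 to 25. True 50%: 0.2273 / 0.4328 = 52.5%. True 60%: 0.1415 / 0.8290 = 17%.
- Wilson, rejection from 24, conflict at 24 only. True 50%: 0.0785 / 0.3601 = 22%. True 60%: 0.0461 / 0.8006 = 6%.

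**Step 4: which interval agrees with the test.** For s responses in 46, the matched 90% limits solve P(reject; s, p) = 0.05 (lower) and 1 − P(reject; s + 1, p) = 0.05 (upper).
- 24/46: 40.1% to 68.0%, excluding 40%, in line with p = 0.0486.
- 23/46: 38.4% to 67.4%, containing 40%, in line with p = 0.077.
- A two-stage 95% interval at 24/46 starts at 37.8%, so adjusting for the stages alone is not enough.
- An ordinary 90% Clopper-Pearson interval at 24/46 starts at 39.2%, so changing the level alone is not enough with that method. Ordinary 90% Wilson (40.3%) and Wald (40.1%) limits do exclude 40% at 24/46, but by numerical accident and not by construction.

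**Step 5: coverage of ordinary 95% intervals under this design**, at true rates of 40, 50, 55 and 60%: Clopper-Pearson 95.9–97.6%, Wilson 93.3–95.4%, Wald 91.6–94.0%.

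**Step 6: average of the observed proportion.**

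| True rate | All outcomes | Trials reaching stage 2 | UMVUE, trials reaching stage 2 |
|---|---|---|---|
| 40% | 37.2% | 45.2% | 55.0% |
| 50% | 46.8% | 52.9% | 58.2% |
| 60% | 58.2% | 61.1% | 63.3% |

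**The case against.** The decision in 7.1 is a response count, and nothing in 7.2 makes the interval a decision tool. A descriptive 95% interval beside a one-sided 5% two-stage test is common practice. It is also stricter than the test on the lower side, so it does not overstate efficacy. Coverage is close to nominal. Section 7.2 does not choose a naive method; it names none, and with Wilson the conflict at 25/46 disappears.

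Most of this stands. It limits the point to a mismatch, and the ordinary interval is the default reading and not stated text. It does not remove the conflict at 24/46, which all three common methods share.

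A reader might go further and infer that the response rate carried into later trials will be too low, because the observed proportion is biased downward. The design does not support that. The downward bias of about 2 to 3 points is an average that includes trials stopped for futility. Among trials that reach stage 2, which are the likelier basis for a larger study, the observed proportion is too high on average. The uniformly minimum variance unbiased estimate (UMVUE) is unbiased over all outcomes but higher still among continuing trials. Its root mean squared error is also larger at true rates of 40% (0.119 against 0.097) and 50% (0.112 against 0.104), and smaller only at 60% (0.095 against 0.100). Making it the headline is a trade-off and not the correction of an error.

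**Conclusion.** The point holds as a mismatch between the reported interval and the test. On the default reading, a trial that rejects 40% can publish an interval containing 40%. With Clopper-Pearson and rejection from 24, this is 43% of rejecting trials at a true rate of 50% and 14% at 60%; with Wilson it is 22% and 6%. Under the written cut-off of 23, the Clopper-Pearson shares are 52.5% and 17%.

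This rests on three assumptions: an ordinary two-sided interval, 16 patients in stage 1, and all 46 patients in the denominator. The accept-or-reject decision is not affected. Two stronger readings, that the interval is invalid or that the estimate passed to later trials is systematically low, are not supported.

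The interval and the cut-off are linked. At exactly 23/46 even the matched interval contains 40%, because rejecting from 23 responses is not a 5% test. Changing the interval alone would leave a conflict there.

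**What to change.** In section 7.2, add after the sentence on the response rate:

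> A two-sided 90% confidence interval by exact stage-wise ordering for the two-stage design, matching the one-sided 5% test, will be reported with the observed proportion. The 95% confidence interval will also be shown as descriptive.

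Name the method for the descriptive interval. The UMVUE may be added as a supplementary estimate (57.3% at 24/46, against an observed 52.2%), but not as the headline.

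In the same amendment, reconcile the rejection cut-off with the stated error rates wherever the rule appears (sections 3.1 and 7.1). Rejecting from 24 responses gives 0.0486 and power 0.80; rejecting from 23 gives 0.077 and 0.83.

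The cost is two sentences in 7.2, the correction to the cut-off, and a few lines of code, with no extra patients or data. The downside is that two intervals appear side by side, so each must be labelled to show which one matches the test.
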